Central venous catheter (CVC) is one of the most commonly used venous access in critically ill children. Continuous access to the central vascular is desirable for administering fluids, drugs, and blood products. However, the wide application of CVC increases the incidence of complications, such as central venous catheter-related bloodstream infection (CLABSI) and central line-associated thrombosis. Studies have shown that CVC-related bloodstream infection increases mortality by 25% [1]. The occurrence of CVC-related bloodstream infection will prolong the hospitalization time of children, increase the medical expenditure of children's families, and even lead to the death of children [2]. In currently published studies, it was found that skin bacterial colonization is one of the important factors leading to CVC-related bloodstream infection [3]. However, most studies focus on the culture of catheter tips, bacterial colonization on the inner surface of dressings, skin bacterial colonization underdressing when extubation and the growth of bacterial film on the inner surface of catheters [4-9], and few studies focus on skin bacterial colonization during placement of indwelling CVC. This trial aims to evaluate the effects of dressing change frequency of CVC on bacterial colonization in pediatric intensive care unit (PICU) in China.

2. Study Objective and Outcomes

2.1 Study Objective

The primary objective is to compare the occurrence of skin bacterial colonization in patients who change dressing after seven days of CVC catheterization versus those who change dressing after 24 hours. The secondary objectives include comparing the incidence of CLABSI and medical adhesive-related skin injury (MRSI) between the two groups during CVC catheterization.

2.2 Outcomes

2.2.1 Primary outcome

The primary outcome is the occurrence of skin bacterial colonization on the seventh or eighth day after CVC catheterization.

- Description:

For patients whose dressing is changed after seven days of CVC catheterization, skin samples will be taken on the seventh day after CVC. For patients whose dressing is changed after 24 hours of CVC catheterization, skin samples will be taken on the eighth day after CVC. The detailed sampling method is shown in the protocol. The colony number above 15 colony-forming units / cm² will be defined as skin bacterial colonization that occurred.

- Time Frame:

The experimental group will be detected on the seventh day after CVC catheterization. The control group will be detected on the eighth day after CVC catheterization.

- Type: binary variable: Yes / No.

2.2.2 Secondary outcomes

(1) Incidence of CLABSI

- Description:

CLABSI will be defined as:

When removing the CVC, the clinical nurse will collect the patient's venous blood sample and sample at the CVC tip. The sampling method is detailed in the protocol. Laboratory personnel independent of the study will report the type of bacteria from blood culture or CVC tip. The Center for Disease Control uses 'definite', 'probable' and 'possible' to distinguish between CRBSI status. This study uses the 'definite'

definition to diagnose CLABSI. The diagnostic criteria for definite CRBSI are the growth of the same pathogen from blood culture of peripheral vein and from the culture of CVC tip or growth of the same pathogen from blood culture of the peripheral vein and from the culture of CVC. The infection department will make a definite diagnosis for CLABSI.

- Time Frame: Time point for CVC removal or suspected bloodstream infection.
- Type: Binary variable: Yes / No.

(2) Incidence of MARSI

- Description:

MARSI is defined as persistent erythema and/or other skin abnormalities (including but not limited to blisters, bullae, erosion, or tear) within 30 minutes or more after the nurse changes the dressing. If the bedside nurse finds a suspected MARSI when changing the dressing, inform the specialist nurse to determine MARSI.

- Time Frame: During CVC catheterization.
- Type: time-to-event outcome.

3. Study Design

3.1 Design

The trial is a multicenter, randomized controlled non-inferiority trial. Patients who fulfill the eligibility criteria outlined in the protocol will be invited to participate consecutively and randomized to the experimental or control group. Block randomization (block size of 4) will be applied.

3.2 Trial Sites

The trial will be conducted in four hospitals in China: Children's Hospital of Fudan University, Xiamen Children's Hospital, Shenzhen Children's Hospital, and Anhui Province Children's Hospital.

3.3 Interventions

3.3.1 Control arm:

Active Comparator: Change the dressing 24 hours after CVC catheterization (CD24h treatment)

Patients in this arm will receive standard dressing change operations. The dressing change will be performed 24 hours after CVC catheterization in the operating room or PICU, and then the second dressing change will be completed seven days later (if there are no clinical indications such as fluid oozing and bleeding). Skin flora sampling will be performed on the eighth day after CVC catheterization. The sampling method is detailed in the protocol.

3.3.2 Experimental arm:

Intervention: Change the dressing seven days after the CVC catheterization (CD7d treatment)

Patients in this arm will change the dressing seven days after the CVC catheterization in the operating room or PICU (if there are no clinical indications such as fluid accumulation and bleeding). Skin flora sampling will be performed on the seventh day after CVC catheterization when the dressing is changed. The sampling method is exactly the same as that of the control group.

3.4 Randomization

Central block randomization with a block size of 4 will be used in this trial. Eligible patients will be randomly assigned to the control arm or the experimental arm (allocation ratio 1:1). According to the seed generated by an independent statistician using SAS software (version 9.4), a sequence of study numbers and randomized allocations will be generated. The allocation sequence will be concealed and placed in the non-transparent sealed envelopes by the independent statistical group from the Clinical Trial Unit (CTU) of the Children's Hospital of Fudan University: the four allocations of each block will be placed in the four sealed small envelopes numbered 1 to 4 in order, and then put into the same large envelope marked with the corresponding block number.

Before each site enrolls the first patient of the block, the coordinator will contact the central coordinator of Children's Hospital of Fudan University, and the central coordinator will assign the envelopes to each site. The clinical nurse in each site will assess the eligibility of the patients and obtain signed informed consent, and then contact the coordinator to obtain the allocation. The coordinator will open the envelopes in numbered order according to the enrollment order, inform the nurse of the allocation, and record the assignment of each enrolled patient.

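### A fixed block size of 4, issued to sites in packets of four, makes up to one third of allocations certain before consent to anyone who knows the earlier allocations in the block

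*SAP*

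**What the plan says.** SAP section 3.1 sets the scheme ("Block randomization (block size of 4) will be applied") and section 3.4 repeats it ("Central block randomization with a block size of 4 will be used in this trial"). The ratio is 1:1, and no variation in block size is mentioned.

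Section 3.4 also fixes the packaging: "the four allocations of each block will be placed in the four sealed small envelopes numbered 1 to 4 in order", and these are "then put into the same large envelope marked with the corresponding block number". A site's coordinator obtains a block's envelopes from the central coordinator before the site enrols that block's first patient. Blocks are therefore completed within a site.

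On roles, section 3.4 says: "The clinical nurse in each site will assess the eligibility of the patients and obtain signed informed consent". Only then does the nurse contact the coordinator, who opens the next envelope and must "inform the nurse of the allocation, and record the assignment of each enrolled patient". Section 3.5 blinds the sample collectors, the laboratory and, while the SAP and programs are being written, the statistician. The enrolling nurse and the coordinator are not on that list. Section 3.5 also holds allocation back from the study team until database lock, which does not fit section 3.4 if the nurse and coordinator belong to that team.

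**The concern.** Sealed opaque envelopes hide the content of the next envelope. They do not stop anyone from working it out from the earlier ones. With a known block of four, the fourth allocation follows from the first three, and the third follows from the first two when those are alike. The packet itself shows its handler the block size and where each block starts. Someone without the packet can count a site's enrolments in fours. The two dressing schedules in section 3.3 also differ visibly on the ward.

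Foreknowledge at the point of judging eligibility or seeking consent allows enrolment to depend on the coming arm, for example through expected catheter stay or skin condition. Such factors could affect colonization. They could also affect whether a day 7 or day 8 sample exists, and section 4.1 drops patients without the primary outcome from the primary analysis. The primary model in section 5.1.1 contains treatment only. A resulting bias could run in either direction relative to the 20-point margin.

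**Working it through.** **Inputs.** Block size 4 and ratio 1:1 (sections 3.1 and 3.4); four sites (3.2); control rate 55%, margin 20 points, one-sided alpha 0.025, power 80%, drop-out 30%, 280 randomized (3.6).

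**The plan's own figure.** The SAP gives no figure for predictability. Its sample size reproduces: n = (1.960 + 0.842)² × 2 × 0.55 × 0.45 / 0.20² = 97.1, so 98 per group; 98 / 0.70 = 140 per group, 280 in all.

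**Certain allocations, full knowledge.** A block has six equally likely orders. An allocation is certain once one arm's two places are used.

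| Position | P(certain) | P(best guess right) |
|---|---|---|
| 1 | 0 | 1/2 |
| 2 | 0 | 2/3 |
| 3 | 1/3 | 1/3 + (2/3)(1/2) = 2/3 |
| 4 | 1 | 1 |

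- Certain share: (0 + 0 + 1/3 + 1) / 4 = 33.3%. In 280 / 4 = 70 blocks this is 70 fourth places plus 70 / 3 = 23.3 third places, about 93 patients.
- Best-guess accuracy: (1/2 + 2/3 + 2/3 + 1) / 4 = 70.8%, against 50% by chance.
- Unfinished last blocks change little. With 70 patients per site (an assumed equal split) there are 17 full blocks each, and 4 × 17 × 4/3 = 91 patients.

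**Certain allocations, partial knowledge.** Suppose a nurse knows each earlier allocation in the block with probability f, and knows the position in the block. Certainty needs both members of the like pair to be known, so the probabilities become f²/3 at position 3 and f² at position 4. The share is (f²/3 + f²) / 4 = f²/3.

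| f | Certain share |
|---|---|
| 1 | 33.3% |
| 0.75 | 18.8% |
| 0.5 | 8.3% |
| 0.25 | 2.1% |

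**Alternatives.** The observer knows all earlier allocations. For varying sizes the observer also knows the menu of sizes but not the current block's size (2,000 simulated runs, 70 patients per site).

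| Scheme | Certain | Best guess |
|---|---|---|
| Fixed 4 | 33.3% | 70.8% |
| Fixed 6 | 25.0% | 68.3% |
| Fixed 8 | 20.0% | 66.6% |
| Random 4, 6 | about 5.5% | about 69% |
| Random 4, 6, 8 | about 2.2% | about 68% |

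**What selection could do (assumed effects, not from the SAP).** Suppose selection at every certain position shifts expected colonization by d points, in opposite directions in the two arms. The bias is 2 × d × certain share.

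- Full knowledge: 2d/3, which is 3.3 points at d = 5 and 6.7 at d = 10.
- f = 0.5: d/6, which is 0.8 and 1.7 points.

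With 98 analysed per group and true rates of 55% and 75%, the standard error is √[(0.55 × 0.45 + 0.75 × 0.25) / 98] = 6.7 points. Under full knowledge, bias favouring the experimental arm would raise the one-sided error from 2.5% to about 7% (d = 5) or 17% (d = 10). Bias the other way would cost power.

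**The case against.** One third is an upper bound. The SAP shows full knowledge only for the coordinator, who opens and records every envelope but is not described as judging eligibility or taking consent. It does not say that one nurse enrols everyone at a site, that nurses share allocations, or that a nurse handles the packet. This stands, and it is why the result is given as a range in f.

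Section 3.1 has patients invited consecutively, and selective enrolment would breach that rule. This also stands, but the rule leaves eligibility to the same nurse and does not prevent prediction. Section 5.1.2 pre-specifies analyses adjusted for age, sex, insertion site, disease type and administration set. These would partly address selection on those factors, but not on expected catheter stay or skin condition.

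Varying block sizes leave most of the guessing advantage: the excess over chance falls only from about 21 points to about 18. That is correct. The gain lies in removing nearly all certain allocations.

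A reader might infer that staff learned the block size from a published plan. The SAP gives no release date relative to enrolment, so that does not follow. It is not needed either, because the packet reveals the size to whoever handles it.

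**Conclusion.** The point holds as a weakness in a stated rule that is cheap to improve. Up to one third of allocations, about 93 of 280, are certain before consent to someone who knows all earlier allocations in the site's current block. The coordinator is in that position. For an enrolling nurse the share is about f²/3 and depends on working practice that the SAP does not describe.

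Two stronger readings are tempting. One is that every enrolling nurse can foresee a third of allocations; the SAP does not establish this. The other is that enrolment was in fact selective, or that the non-inferiority result is biased. Predictability creates the opportunity only. The bias figures above rest on assumed effects and on selection at every certain position.

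**What to change.** For all blocks not yet issued, have the independent statistician generate the list within site with randomly varying block sizes, for example 4, 6 and 8. Supply each site with one consecutively numbered series of envelopes, without block packets or block labels. Keep the sizes out of documents that site staff can read. Certain allocations then fall from 33.3% to about 2%, or about 5.5% with sizes 4 and 6 only.

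The cost is regenerating and repacking the remaining list, plus a replacement for the present supply by block. The largest possible imbalance within a site at any moment rises from 2 to 4 patients when a block of 8 is in use (half the block size).

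If all blocks have been issued, add block number and position to the dataset from the coordinator's record, since the variable list in section 7 has neither. Then compare baseline characteristics between arms among the predictable positions: every fourth place, and third places that follow two like allocations. With about 93 such patients this check will miss modest selection, and it cannot see factors that were not recorded.

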3.5 Blinding

The sample collectors and laboratory personnel will be blinded to the assignment of the patients. The trial statistician will also be blinded regarding the treatment code when developing the statistical analysis plan and writing the statistical programs. The actual allocation will only be provided to the study team after the database lock.

3.6 Sample Size

This study is a non-inferiority design, and the primary outcome is the occurrence of skin bacterial colonization on the seventh or eighth day after CVC catheterization (binary outcome). The sample size is calculated based on the difference between the two groups of the primary outcome.

According to our previous pilot study that included 49 subjects, the occurrence of skin bacterial colonization in the CD7d group and the CD24h group was 56.3% and 55.6%, respectively. A non-inferiority margin of 20% is considered to be clinically acceptable. Based on the assumptions of (i) the occurrence of skin bacterial colonization of 55% in the CD24h group, (ii) the non-inferiority margin of 20%, (iii) power of 80%, and (iv) a one-sided alpha of 0.025, the sample size estimation resulted in 98 subjects per group (calculated with PASS software, version 16.0). Considering a 30% drop-out rate, a total of 280 subjects should be randomized (140 per group).

4. Analysis Populations

4.1 Study population data sets

Two study populations will be considered in the analysis as follows:

- **Intent-to-Treat population**

Intent-to-treat (ITT) population will be defined at the moment the randomization is performed. For example, if a participant receives the wrong treatment or no treatment at all or is lost for follow-up for outcomes, he/she will be analyzed according to the arm to which they were allocated. This will be the primary analysis for the trial. Participants will be excluded from the ITT analysis if the primary outcome is missing, forming a modified ITT population (mITT).

- **Per-protocol population**

Per-protocol (PP) population will only include patients who received the treatments according to the protocol. In addition, the patients in the CD7d group completed skin sample collection on the seventh day after CVC catheterization, and the patients in the CD24h group completed it on the eighth day.

Participants will be excluded from the PP population if they:

- Did not adhere to per-protocol treatment, including the CD7d group changing the dressing less than seven days after CVC catheterization, or the CD24h group does not change the dressing more than 24 hours after CVC catheterization.
- Switched treatment.

This population will be used for the supportive analyses.

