5.1. Primary Outcome Analysis

5.1.1 ITT analysis of the primary outcome - the primary analysis

The primary outcome is a binary outcome: the occurrence of skin bacterial colonization on the seventh or eighth day after CVC catheterization. The primary analysis will be based on the ITT population as defined above.

Hypothesis: Let π_1 denote the occurrence of skin bacterial colonization on the eighth day after CVC catheterization in the CD24h group (control group), and let π_2 denote the occurrence of skin bacterial colonization on the seventh day in the CD7d group (experimental group), the non-inferiority margin $\Delta=20\%$. The null hypothesis is $H_0: \pi_2 - \pi_1 > \Delta$ versus the alternative hypothesis is $H_A: \pi_2 - \pi_1 \leq \Delta$.

A generalized linear model (GLM) will be used to test the above hypothesis. In the GLM, the occurrence of skin bacterial colonization will be treated as the dependent variable and the treatment as the fixed effect, following a binomial distribution and identity link function. A point estimate of risk difference between groups in the difference and its 95% confidence interval (CI) will be estimated. CD7d treatment will be considered non-inferior to the CD24h treatment if the upper 95% confidence limit is no greater than Δ , where $\Delta= 20\%$, the predetermined non-inferiority margin.

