5.1.2 Sensitivity analyses of the primary outcome

- PP analysis with GLM (described in 5.1.1) will be performed.
- An analysis of the primary outcome will be adjusted for age, gender, CVC catheterization site, type of disease, and administration set at baseline in ITT and PP population, respectively. The adjusted difference and 95% one-sided upper limit comparing the two groups will be derived by GLM (described in 5.1.1). If the above identity-binomial GLM does not converge when all covariates are introduced into the model, the adjusted model will be performed by removing a covariate one by one until the model converges.

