5.2. Secondary Outcome Analysis

All secondary outcomes will be analyzed as a superiority design, and two-sided 95% CIs for the differences in these outcomes between two groups will be calculated. Secondary outcome analyses will be based on the ITT population unless specified.

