5.2.4 Handling of Missing data

Different data imputation methods will be used according to the reasons for the missing data. For randomly missing data, such as vital signs, laboratory indicators, auxiliary examinations, etc., multiple imputations (MI) will be used to impute the missing data for analyses of secondary outcomes.

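### The primary analysis labelled ITT is a complete-case analysis with no check for swabs missing in relation to the outcome, and the population for CLABSI and MARSI is unclear

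*SAP*

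**What the plan says.** Section 4.1 announces two populations, ITT and per-protocol. The ITT set is fixed at randomisation, and a child who gets the wrong treatment, gets none, "or is lost for follow-up for outcomes, he/she will be analyzed according to the arm to which they were allocated". The same paragraph then says: "Participants will be excluded from the ITT analysis if the primary outcome is missing, forming a modified ITT population (mITT". The name mITT does not appear again. Section 5.1.1 states: "The primary analysis will be based on the ITT population as defined above". Table 2 (section 6.2) labels the primary row ITT.

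The sensitivity analyses in section 5.1.2 are of two kinds:
- **Per-protocol:** "PP analysis with GLM (described in 5.1.1) will be performed". Section 4.1 requires for this set that "the patients in the CD7d group completed skin sample collection on the seventh day after CVC catheterization", with the matching day-8 requirement for CD24h.
- **Covariate-adjusted models** in the ITT and PP sets, with no imputation of the outcome.

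Section 5.2.4 limits imputation: "multiple imputations (MI) will be used to impute the missing data for analyses of secondary outcomes". Section 3.6 reads: "Considering a 30% drop-out rate, a total of 280 subjects should be randomized (140 per group". For CLABSI and MARSI, section 5.2 says: "Secondary outcome analyses will be based on the ITT population unless specified".

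**The concern.** The two statements in section 4.1 cannot both apply to a child with no swab: one keeps the child in the analysis and the other removes the child. The second prevails for the primary outcome, so the analysis is complete-case under an ITT label.

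Inflating the sample for drop-out protects power, not validity. If the chance of having a swab on day 7 or 8 is related to colonisation, and differently so by arm, the risk difference among sampled children is not the one among randomised children. Every row of Table 2 uses observed swabs only, so none can show whether a non-inferiority conclusion survives plausible assumptions about the others.

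The label also carries into section 5.2. Read literally, section 4.1 could drop children without a swab from CLABSI and MARSI, although neither outcome needs it. Under section 2.2.2, CLABSI is assessed at catheter removal or suspected infection and MARSI during catheterisation. Two readings give two denominators, and the choice would be made after the data are seen.

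**Working it through.** **1. The plan's own figure.** From section 3.6: 55% in both arms, margin 0.20, one-sided alpha 0.025, power 80%.

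n = (1.960 + 0.842)² × 2 × 0.55 × 0.45 / 0.20² = 97.1, so 98 per arm. Then 98/0.70 = 140 per arm, 280 in total. The stated size is reproduced. At that allowance 0.30 × 140 = 42 per arm, 84 in all, could be left out.

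**2. False non-inferiority when the outcome affects missingness.** Rule from section 5.1.1: declare non-inferiority if U = d + 1.96 × √[p_T(1−p_T)/n + p_C(1−p_C)/n] ≤ 0.20. Assumptions, not in the SAP: true rates 55% (CD24h) and 75% (CD7d), 140 randomised per arm, the same total fraction missing, m, in both arms.

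Let q1 and q0 be the chances of a missing swab for colonised and non-colonised children, with p·q1 + (1−p)·q0 = m and a chosen odds ratio (OR) of q1 to q0. The observed rate is p(1−q1)/(1−m). Example for CD7d with m = 0.30: q1 = 0.35 and q0 = 0.15 give 0.75 × 0.35 + 0.25 × 0.15 = 0.30 and OR = (0.35/0.65)/(0.15/0.85) = 3.05. The observed rate is 0.75 × 0.65/0.70 = 0.696, and the rate among the missing is 0.75 × 0.35/0.30 = 0.875.

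Exact binomial enumeration with 98 observed per arm gives 2.4% when swabs are missing at random. Otherwise:

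| OR | Observed CD24h / CD7d | Both arms | CD7d only | Inverse OR, both arms | Inverse OR, CD7d only |
|---|---|---|---|---|---|
| 1.66 | 0.513 / 0.723 | 1.7% | 5.8% | 3.3% | 0.76% |
| 3.05 | 0.472 / 0.696 | 1.0% | 12.1% | 4.3% | 0.13% |
| 7.40 | 0.424 / 0.670 | 0.4% | 21.8% | 5.3% | below 0.01% |

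In the CD7d-only columns the observed control rate stays at 0.55. The CD7d-only column with OR above 1 implies that missing CD7d children are 81%, 87% and 94% colonised, against 55% of missing controls.

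With less missing, at OR 3.05 (both arms / CD7d only): 1.3% / 7.7% at 20% missing (112 observed per arm) and 1.8% / 4.5% at 10% (126 observed).

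**3. Tipping point, imputed values treated as observed.** Take 54/98 colonised in each arm. The completer limit is 1.96 × √(2 × 0.551 × 0.449/98) = 13.9%, so non-inferior. Fill the 42 missing controls at 23/42 (55%) and raise the count among the 42 missing CD7d children:
- 34/42: U = 19.4%, still non-inferior.
- 35/42 (83%): d = 89/140 − 77/140 = 0.0857; U = 0.0857 + 1.96 × √[(0.636 × 0.364 + 0.55 × 0.45)/140] = 20.04%, reversed.
- Extreme case, all missing CD7d and no missing CD24h colonised: 96/140 − 54/140 = 30.0%, 95% CI 18.9% to 41.1%.

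**4. Tipping point with multiple imputation.** Rates are drawn by arm from beta(x + 0.5, n − x + 0.5), a shift delta is added for missing CD7d children, and Rubin's variance is used. Missing controls are taken to be like observed controls.

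| Missing | Completers, CD7d vs CD24h | Completer upper limit | Tips when missing CD7d rate is about |
|---|---|---|---|
| 30% | 54/98 vs 54/98 | 13.9% | 77% (delta +22 points) |
| 30% | 58/98 vs 54/98 | 17.9% | 67% (delta +8 points) |
| 20% | 62/112 vs 62/112 | 13.0% | 93% |
| 20% | 66/112 vs 62/112 | 16.5% | 78% |
| 10% | null or 4-point difference | below 20% | no tip for shifts up to 45 points |

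The fourth row is sensitive to rounding of the 4-point difference: 67/112 vs 62/112 tips at about 74%.

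**The case against.** The best case for the plan has five parts.

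- **The exclusion is disclosed.** Section 4.1 states it and names it, and section 5.1.1 refers back to that definition, so the analyst has no discretion over the primary set. This stands: for the primary outcome the definitional fault is one of labelling and one contradictory sentence.
- **The adjusted model gives partial cover.** If missingness depends only on arm and the listed covariates, a correctly specified adjusted complete-case model is valid for the adjusted difference. This also stands, although section 5.1.2 lets covariates be dropped until the model converges. The gap is missingness that depends on the unseen outcome, which nothing addresses.
- **Reasons are partly planned.** Figure 1 will show withdrawal reasons and numbers available per population. A withdrawal reason is not quite a reason for a missing swab, and section 7 lists no variable for the latter, so this reduces the request without removing it.
- **The alarming rates need a one-armed mechanism.** No section supports outcome-dependent loss in CD7d alone. The inverse pattern is strongly conservative, as is a shared pattern in which colonised children are lost more often. This is correct, and it is why the direction of bias cannot be assumed.
- **30% is a drop-out allowance, not a forecast of missing swabs.** True. At 10% missing neither completer result tipped. The 8-point tip also starts from a completer limit of 17.9%, already close to the margin.

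These points limit the size of the concern. They do not supply the missing analysis.

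**Conclusion.** The concern holds and should be fixed. The primary analysis is complete-case under an ITT label, section 4.1 contradicts itself on children lost to follow-up, and no planned analysis tests outcome-dependent missing swabs. The population for CLABSI and MARSI can be read two ways.

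The effect on the conclusion depends on how many swabs are missing and why, and the SAP states neither. At 30% missing, a result close to the margin could be overturned by a modest difference between missing and sampled CD7d children; at 10% the results examined were robust. All scenarios assume equal missingness in the two arms and the rates stated above. The sample-size arithmetic is correct and is not in question.

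**What to change.** 1. In section 4.1, define ITT as all randomised patients and list mITT as its own population. Label the primary set mITT in section 5.1.1 and Table 2. The complete-case analysis can stay primary.
2. In section 5.1.2, add one pre-specified sensitivity analysis for missing outcomes. Impute bact_coloni by arm from baseline covariates (centre, age, gender, disease type, CVC site), with a delta shift varied in both arms until the upper limit crosses 20%. Leave catheter dwell time out of the imputation model: it arises after randomisation, and a child whose catheter came out before sampling has no sampled counterpart with the same dwell time.
3. Report the number of missing swabs and the reasons by arm, and add a variable for the reason to section 7. State that values imputed after early catheter removal are hypothetical.
4. In section 5.2, state that CLABSI and MARSI are analysed in all randomised patients whether or not a day-7 or day-8 swab exists.

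The cost is SAP wording, one variable and a few extra analyses. The sensitivity interval may be wider than the primary one and will rest partly on hypothetical values. No extra patients are needed.

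### The SAP does not settle whether patients without a day-7/8 skin sample stay in the CLABSI and MARSI analyses, so observed events may be dropped

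*SAP*

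**What the plan says.** Section 4.1 announces two sets, ITT and per-protocol: "Two study populations will be considered in the analysis as follows". Three statements under ITT bear on this point:

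- The set is fixed at randomization: "Intent-to-treat (ITT) population will be defined at the moment the randomization is performed".
- A participant who, among other examples, "is lost for follow-up for outcomes, he/she will be analyzed according to the arm to which they were allocated".
- A missing primary outcome leads to exclusion: "Participants will be excluded from the ITT analysis if the primary outcome is missing, forming a modified ITT population (mITT"). The term mITT is not used again in the SAP.

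For the primary outcome, section 5.1.1 says: "The primary analysis will be based on the ITT population as defined above". Table 2 labels the corresponding row ITT population.

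For the secondary outcomes, section 5.2 says: "Secondary outcome analyses will be based on the ITT population unless specified". Sections 5.2.1 (CLABSI) and 5.2.2 (MARSI) name no other set.

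The outcomes run on different clocks. The primary outcome is a skin sample on day 7 (CD7d) or day 8 (CD24h). For CLABSI, section 2.2.2 gives "Time Frame: Time point for CVC removal or suspected bloodstream infection". For MARSI, the same section gives the whole period of catheterization.

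**The concern.** Whether a skin sample was obtained on day 7 or 8 has no bearing on whether CLABSI or MARSI was observed. If the missing-sample exclusion carries over to the secondary analyses, patients with known CLABSI or MARSI status are discarded for an unrelated reason.

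The loss need not be random. Suspected infection may lead to catheter removal, removal before the sampling day probably means no sample, and no sample would mean exclusion. The outcome event could then cause its own removal from the analysis. The condition for staying in also falls one day later in CD24h than in CD7d, so the selection is not identical in the two arms. For MARSI, a Cox model would be fitted to patients selected on something that happens after randomization.

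CLABSI and MARSI are the only secondary outcomes, and they carry the comparison of harms for the longer dressing interval. Their denominators should not depend on how an analyst reads one label.

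**Working it through.** **1. The plan's own numbers (section 3.6).** Inputs: colonization 55% in CD24h, taken as equal in CD7d; margin 20%; one-sided alpha 0.025; power 80%; 1:1 allocation (section 3.4); drop-out 30%.

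- n per group = (1.960 + 0.842)² × 2 × 0.55 × 0.45 / 0.20² = 7.85 × 0.495 / 0.04 = 97.1, rounded up to 98. This matches the SAP.
- With drop-out: 98 / (1 − 0.30) = 140 per group, 280 in total. This matches "Considering a 30% drop-out rate, a total of 280 subjects should be randomized (140 per group").

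The primary sample size already allows for the loss, so this point does not change it.

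**2. Which set does the label ITT population denote?**

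- *Reduced set.* The exclusion stands inside the ITT entry, and only two sets are announced. Section 5.1.1 and Table 2 use the label for the primary analysis. Section 5.2.4 limits multiple imputation to the secondary outcomes, so patients without a primary outcome cannot enter that analysis. In those two places the label must mean the set left after exclusion. Section 5.2 uses the same label.
- *All randomized.* The population is fixed at randomization. The exclusion is worded for the ITT analysis, not the ITT population, and yields a set with its own name. Section 5.2 refers to the population and does not mention mITT.

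Both readings follow the text.

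**3. Two illustrative patients.**

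| Patient | Secondary outcome | Day-7/8 sample | Reduced set | All randomized |
|---|---|---|---|---|
| CVC removed on day 5 for suspected infection, CLABSI confirmed | Known | None | Event dropped | Event counted |
| CD24h, MARSI at the 24-hour change, CVC out before day 8 | Known | None | Event dropped | Event counted |

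Both rows assume that removal before the sampling day leaves the primary outcome missing.

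**4. Size of the difference in denominators.** Patients left out = 280 × proportion without a primary outcome.

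| Proportion without outcome | Left out | Remaining |
|---|---|---|
| 10% (assumed) | 28 | 252 |
| 20% (assumed) | 56 | 224 |
| 30% (whole planned drop-out) | 84 (42 per arm) | 196 (98 per arm) |

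**5. Share of patients with events left out.** The SAP gives no CLABSI or MARSI rate, so only a relative figure is possible. Let k be the event risk in excluded patients divided by that in retained patients (assumed). At 30% excluded:

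share = 84k / (196 + 84k)

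- k = 0.5: 42 / 238 = 18%
- k = 1: 84 / 280 = 30%
- k = 2: 168 / 364 = 46%
- k = 3: 252 / 448 = 56%

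These figures apply only under the reduced-set reading, and only if the secondary outcomes were in fact observed in all 84 patients.

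**The case against.** The strongest reply is that section 5.2 already says what is wanted: it names the ITT population, which section 4.1 fixes at randomization, while the exclusion creates a separate mITT set for the primary analysis. Two other passages lean the same way. Section 6.1 bases percentages on patients with data available, and section 5.2.4 plans multiple imputation for secondary outcomes. This stands as a legitimate reading. It does not settle the matter, because section 5.1.1 and Table 2 use the identical label for the reduced set. Moreover, a rule for percentage denominators or for imputation does not determine who belongs to an analysis set.

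Section 4.1 also excludes patients whose primary outcome is missing, which is not the same as having no sample on the exact day. The per-protocol definition adds sampling on day 7 or 8 as a further requirement, which suggests that samples from other days might count in the ITT analysis. The SAP does not say how early catheter removal is classified. This stands: the link from early removal to a missing outcome is an inference from the fixed sampling days.

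On MARSI, the SAP identifies events at dressing changes and schedules none before day 7 in CD7d. Few first-week events in that arm would largely reflect this schedule. Nothing in the SAP says that MARSI leads to catheter removal. This also stands, and it makes the self-exclusion argument weaker for MARSI than for CLABSI.

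Finally, section 3.6 does not say what makes up the 30% drop-out. Some of those patients may lack secondary outcomes too.

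**Conclusion.** The point holds as an unresolved ambiguity with a real consequence. A stated rule, applied consistently under one literal reading, would drop observed CLABSI and MARSI events for lack of a skin sample. Under another literal reading it would not. Two analysts could work from 280 patients and from about 196, and both would be following the SAP.

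A reader might infer that the SAP definitely leaves these events uncounted, that every early catheter removal is a missing primary outcome, or that a low CLABSI count would be produced by the exclusion. The text does not support any of these. Events may be uncounted; how early removals are classified is not stated; and no event rates are given.

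The figure of 84 of 280 is an upper limit under the planned drop-out, reached only if all of it lacks a sample. The number of events affected is unknown. The non-inferiority conclusion, its margin and the sample size are untouched, and the secondary outcomes do not decide the trial. The text should be corrected, but the defect does not undermine the primary analysis.

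**What to change.** - **Section 4.1:** list mITT as a separate set, defined as randomized patients with an observed primary outcome. Limit the missing-outcome exclusion to the primary-outcome analysis. Keep ITT for all randomized patients.
- **Section 5.1.1 and Table 2:** use the label mITT where that set is meant.
- **Section 5.2:** state that CLABSI and MARSI are analysed in all randomized patients as allocated, regardless of whether a skin sample was obtained. MARSI follow-up runs from catheterization and is censored at CVC removal.
- **Tables 3 and 4:** use these denominators.

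The cost is a few sentences and table labels. No extra patients or visits are needed: section 2.2.2 already ascertains both outcomes up to catheter removal, and section 4.2 closes data collection when the last CVC is out. The event and removal dates needed for MARSI are already required by the planned Cox model. The change should be made before allocation is released after database lock (section 3.5).
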